1.1 Background

Peripheral T-cell lymphomas (PTCLs) are a heterogeneous, often aggressive, group of non-Hodgkin lymphomas (NHL) comprising about 5% to 10% of all new NHL diagnoses. The most common subtypes are peripheral T-cell lymphoma not otherwise specified (PTCL-NOS), angioimmunoblastic T-cell lymphoma (AITL), and anaplastic large-cell lymphoma (ALCL). Recent advances in understanding normal T-cell biology together with gene expression and immunohistochemistry studies have suggested that a group of PTCL are derived from the CD4⁺ T-cell subset, follicular helper T-cells (Tfh), which are characterised by surface expression of PD-1 and inducible co-stimulator (ICOS) and nuclear expression of BCL6¹⁻⁴. The ligand of PD-1, PD-L1, is expressed on both lymphoma cells and stromal cells⁵. Historically the therapeutic approaches for PTCL have been derived from standard treatments for various subtypes of aggressive B-cell lymphoma. However, outcomes remain poor when these strategies are used in the management of PTCL, with 5-year overall survival (OS) ranging from 25 to 35% for the common subtypes and excluding ALK-positive ALCL⁶.

Four drugs have been approved by the US Food and Drug Administration (FDA) for treatment of relapsed PTCL: pralatrexate, romidepsin, brentuximab vedotin (approved for ALCL only), and belinostat. In the relapsed/refractory setting, rates of response to single-agent therapy with these drugs (other than use of brentuximab vedotin for ALCL) range from 20% to 35%⁷⁻¹⁰.

Several mechanistically based therapies are currently in clinical trials for T-cell lymphoma. In patients with ALK-positive ALCL there are efforts to study crizotinib, which has been approved for treatment of lung cancer harboring a translocation in the *ALK* gene. As ALK is constitutively expressed in a subset of patients with ALCL, this is an attractive therapeutic target. In small series of relapsed patients, response rates of 60% to 100% to crizotinib have been seen, including one study of 11 patients (9 with ALCL) showing an overall response rate (ORR) of 91%¹¹. Several other ALK inhibitors are also in development but primarily these agents are being investigated in lung cancer.

IDH2 is an enzyme that normally catalyses the conversion of isocitrate to alpha-ketoglutarate (α-KG) in the Krebs cycle. Mutations in the *IDH2* gene are seen in several malignancies, including acute myeloid leukemia (AML), gliomas and glioblastoma, chondrosarcoma, and cholangiocarcinoma. Recently a phase I study of the oral IDH2 inhibitor AG-221 in patients with AML and myelodysplastic syndrome (MDS) showed an ORR of 56% in 45 patients, including complete and durable responses¹². Gain-of-function mutations in *IDH2* are seen in 20% to 45% of cases of AITL and rarely in PTCL-NOS^{13,14}. Early-phase studies of AG-221 in malignancies harboring an *IDH2* mutation, including disease-specific cohorts of AITL, are underway (ClinicalTrials.gov ID: NCT02273739).

Phosphatidylinositol 3-kinase (PI3K) inhibitors and their downstream targets (eg, AKT or mammalian target of rapamycin [mTOR]) are important in cell differentiation, metabolism, survival, and proliferation. Idelalisib is a PI3K-delta inhibitor currently approved for chronic lymphocytic leukemia/small lymphocytic lymphoma, and follicular lymphoma and many other PI3K inhibitors are being developed and investigated^{15,16}. The PI3K-delta/gamma inhibitor duvelisib (IPI-145) has demonstrated an ORR of 53% in PTCL¹⁷.

Another pathway of therapeutic interest in PTCL is the Janus kinase/signal transducer and activator of transcription (JAK/STAT) pathway; this is because mutations in *JAK3* have been seen in natural killer (NK)-cell/T-cell lymphomas, and activation of the JAK/STAT signaling pathway has also been described in PTCL^{13,14}. Ruxolitinib, approved for treatment of myeloproliferative neoplasms, is being investigated in relapsed lymphoma, including PTCL (ClinicalTrials.gov ID: NCT01431209).

Studies incorporating these novel agents as part of upfront treatment regimens are underway, and there is hope for improved responses.

1.2 Trial Rationale

1.2.1 Justification for patient population

The outcome for patients with relapsed / refractory PTCL is extremely poor, with a median survival of just 6-18 months and very few patients cured of their disease¹⁸. Therefore although these patients are uncommon, there is a significant unmet medical need and a requirement for rational drug combinations with validated predictive biomarkers.

1.2.2 Justification for design

Avelumab is currently in clinical development across phases 1-3 with safety data in relation to its use in solid tumours (see Investigator's Brochure (IB) for Avelumab). Avail-T has been designed as a single arm phase 2a study on the assumption that the safety profile obtained with avelumab in patients with solid cancers will be essentially the same as for patients with hematological malignancy.

Other considerations were to produce a study to determine the primary outcome measures (as listed below) including best overall response rate during 8 cycles (each cycle being 28 days) of treatment as rapidly as possible in this rare disease population but also with the flexibility to deliver a larger study.

In order to fulfill these criteria we propose a Bayesian probability plot approach.

1.2.3 Choice of treatment

Cross-linking of PD-1 has been shown to inhibit T-cells¹⁹ and this has prompted interest in perturbing PD-1/PD-L1 signaling in order to enhance T-cell anti-tumour activity in solid cancers^{20,21}. However, this model does not appear to explain PD-1/PD-L1 function in Tfh-cells, a CD4⁺ T-cell subset required for germinal centre formation, in part, by providing IL-4 and IL-21 to cause B-cell proliferation^{22,23}. Data from mice lacking PD-1 demonstrates important functions for this surface protein in T-cell differentiation^{24,25}. While the earlier study²⁴ demonstrated that PD-1 deficient animals had increased follicular T-cells there was a paradoxical lack of increased functions attributable to the Tfh subset. Subsequent work following identification of a repressive follicular T-cell subset (Tfr)²⁵ has provided a resolution for this problem: PD-1^{-/-} mice show increased numbers and functions of Tfr whilst Tfh are repressed. Interestingly, mice lacking the PD-1 ligand (PD-L1) demonstrated the same phenotype. This suggests that *in vivo* the PD-1/PD-L1 axis regulates the differentiation of follicular T-cells such that stimulation of PD1 drives Tfh differentiation whereas blockade of PD-1/PD-L1 produces a repressive and Tfr dominated environment.

PD-L1 is expressed on both tumour and stromal components of PTCL (Table 1)⁵ by immunohistochemistry, which is likely to underestimate patients for which the PD-1/PD-L1 axis is functionally important. Avelumab, in distinction from other therapeutic anti-PDL1 antibodies causes antibody dependent cellular cytotoxicity (ADCC)²⁶. Therefore, avelumab may deplete essential stromal components of the tumour microenvironment as well as causing apoptosis of lymphoma cells.

Table 1

Percentage of cases expressing PD-L1 on tumour cells and stroma in PTCL (from Wilcox et al.⁵). Cutaneous PTCL have been excluded from the data.

	Tumour PD-L1 (%)	Stroma PD-L1 (%)
PTCL-NOS	17	43
AITL	5	57
ALK+ ALCL	33	22
ALK-ALCL	15	35
Other	10	24

EMR 100070-001 is a study of avelumab in metastatic and locally recurrent solid tumours. None of the patients treated with doses up to 10 mg/kg experienced a dose limiting toxicity and this dose is, therefore, considered a safe and well-tolerated dose (Avelumab Investigators Brochure v4.0, February 2015).

A dose-escalation trial of avelumab (MSB0010718C)²⁷ has been reported and investigators demonstrated that this antibody could be safely administered in doses up to 20 mg/kg every 2 weeks.

480 patients have been enrolled in 11 expansion cohorts and treated with avelumab 10 mg/kg every 2 weeks up to November 2014. 59/480 (12.3%) had at least one treatment related adverse event of > grade 3 – anaemia, fatigue, gammaGT increase, infusion related reactions lipase increase, lymphocyte count decreased, autoimmune hepatitis, constipation, dyspnoea, hypertension, hypokalaemia, hypoxia, pneumonitis, vomiting. 56/480 (11.7%) had potential autoimmune related adverse events. As of November 2014 49/480 patients (10.2%) experienced at least one infusion

related reaction most of which were grade 1 or 2. Two suspected unexpected serious adverse reactions (SUSARs) (infusion-related reaction (IRR) and anaphylaxis) were reported following which a premedication regime of piriton and paracetamol was mandated.

In a "real-world" study of outcomes in PTCL the median OS after relapse/progression in 211 patients initially responding (PR or CR) to primary treatment was 6.0 months and among patients with primary refractory disease (n = 143), median OS from response evaluation was only 2.5 months²⁸. One trial in refractory/relapsed PTCL administered treatment for 6 months²⁹, while the current UK trial, RomiCar, administers 8 cycles of treatment. We, therefore, chose a regimen that allows for 8 months treatment with avelumab.

For complete details of the *in vitro* and non-clinical studies refer to the avelumab IB.

2. AIMS, OBJECTIVES AND OUTCOME MEASURES

2.1 Aims and Objectives

Identify overall response to avelumab in relapsed/refractory PTCL.

2.2 Outcome Measures

Primary Outcome Measures

- Best overall response (PR + CR) during 8 cycles of treatment using Revised Response Criteria for Malignant Lymphoma²⁷

Secondary Outcome Measures

- Toxicity using CTCAE v4
- Best overall response (PR + CR) at any time of treatment using Revised Response Criteria for Malignant Lymphoma²⁷
- OS
- PFS
- Reduction in tumour size measured as maximum percentage change in the radiological sum of the product of the diameters of up to 6 target lesions from baseline
- Duration of response from time of first documented response until relapse, progression or death

Exploratory Outcome Measures

- PD-L1 expression levels
- Cell free DNA analysis
- Immunophenotyping
- Biomarkers of response

3. TRIAL DESIGN

This is a single arm phase 2a trial to determine responses to avelumab in patients with refractory and relapsed PTCL. A single arm study has been selected to determine evidence of activity in PTCL to further evaluate in a larger trial. Patients will be recruited over a 24-month period and will receive 8 cycles of treatment with the possibility of continued treatment if the patient is showing clinical benefit. Patients will continue to be followed up for progression and survival for one year after the end of the trial treatment.

The trial will enrol 30 patients with the flexibility to enrol more, up to 35, if required. Based on 30 patients in the trial, if 11 responses were obtained this would give a probability of 60% that the response rate is greater than 35%. If 13/30 responses were obtained there is a probability of 84% that the response rate is greater than 35%. Other possible outcomes, both for 30 and 35 patients, have been plotted and are presented (Appendix 2).

4. ELIGIBILITY

4.1 Inclusion Criteria

- Male or female patients aged ≥ 16 years
- Life expectancy > 12 weeks
- ECOG performance status ≤ 2
- Relapsed or refractory* peripheral T-cell lymphoma including the following histologies: peripheral T-cell lymphoma not otherwise specified (PTCL NOS), angioimmunoblastic T-cell lymphoma (AITL), anaplastic large cell lymphoma (ALCL), enteropathy associated T-cell lymphoma (EATL), extranodal NK/T- cell lymphoma (ENKL), transformed mycosis fungoides (LCT MF), and subcutaneous panniculitis and T cell lymphoma * For all relapsed patients, relapse must be confirmed by tissue biopsy (or bone marrow trephine if no other tissue available). For relapsed and refractory patients, a biopsy must have been obtained within the last 3 months of registration
- Failed at least 1 prior therapy (but no upper limit of prior regimens)
- Adequate haematological function defined by the following at registration:
 - absolute neutrophil count (ANC) $\geq 1.0 \times 10^9/L$ (unsupported)
 - platelet count $\geq 75 \times 10^9/L$ (unsupported)
 - haemoglobin $\geq 90 \text{ g/L}$ (may have been transfused)
- Adequate hepatic function and no evidence of hepatic involvement by T-cell lymphoma as defined by:
 - total bilirubin level $\leq 1.5 \times$ the upper limit of normal (ULN) range (patients with elevated bilirubin due to Gilbert's syndrome are eligible)
 - AST and ALT levels $\leq 1.5 \times$ ULN for all patients **and**
 - no clinical suspicion of hepatic involvement by T-cell lymphoma and
 - no liver abnormalities on imaging studies that might be due to T-cell lymphoma
- Adequate renal function defined by an estimated creatinine clearance $\geq 30 \text{ mL/min}$ according to the Cockcroft-Gault formula (or local institutional standard method)
- CT measurable disease with at least 1 lesion having short axis $> 1.5\text{cm}$ or splenomegaly $> 14\text{cm}$ in cranio-caudal length attributable to relapsed/non responding lymphoma
- Negative serum pregnancy test at screening for women of childbearing potential.
- Highly effective contraception for both male and female patients if the risk of conception exists. (Note: women of childbearing potential and men able to father a child must agree to use 2 highly effective contraception, defined as methods with a failure rate of less than 1 % per year. Highly effective contraception is required from consent, throughout and for at least 60 days after avelumab treatment.
- Ability to give informed consent

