7. TREATMENT DETAILS

7.1 Trial Treatment

All patients registered to the trial will receive avelumab at the dose of 10 mg/kg by intravenous (IV) infusion once every 2 weeks for 8 cycles (28 day cycles). Each infusion of avelumab should be delivered over 1h (-10/+20min) unless IRR is experienced (see Table 3). Avelumab dose should be prepared in accordance with the NHS England National Dose Banding Table for avelumab (please refer to the pharmacy manual)

All patients should be weighed within 3 days prior to day 1 dosing for every cycle to ensure they did not experience either a weight loss or gain >10% from the weight used for the last dose calculation. For weight change less than 10% the decision to recalculate the avelumab dose can be in accordance with institutional practice. If the patient experienced either a weight loss or gain >10% compared to the weight used for the last dose calculation, the amount of study drug must be recalculated.

Premedication

Premedication with an antihistamine and with paracetamol, to mitigate IRRs and is **mandatory** approximately 30 to 60 minutes prior to the first four doses of avelumab (Cycles 1-2), but may continue to be administered for subsequent cycles based upon clinical judgment and presence/severity of prior infusion reactions, at the treating Investigator's discretion. For example, 25-50 mg diphenhydramine and 500-650 mg paracetamol IV or oral equivalent should be considered.

This regimen may be modified based on local treatment standards and guidelines as appropriate provided it does not include systemic corticosteroids.

Avelumab should be administered in a setting that allows for immediate access to an intensive care unit or equivalent environment and administration of therapy for anaphylaxis, such as the ability to implement immediate resuscitation measures. Steroids (dexamethasone 10 mg), epinephrine (1:1,000 dilution), allergy medications (IV antihistamines), bronchodilators, or equivalents, and oxygen should be available for immediate access.

Following avelumab infusions, patients must be observed for 2 hours post-infusion for potential IRRs.

Patients will be assessed during the course of treatment, at progression or after completion of 8 cycles of treatment as described in section 7.3.

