7.2 Treatment Schedule

Avelumab 10 mg/kg will be administered once every 14 days for a proposed duration of 8 cycles (28 day cycles), (16 doses).

If the patient is showing clinical benefit following 8 cycles of trial treatment patients may continue to receive avelumab treatment at the treating Investigator's discretion, until loss of response, toxicity, or death.

Every effort should be made for patients to attend on the scheduled visit days. However, if a patient is unable to attend on the specified day, assessments may be scheduled for +/- 3 days.

The full blood count should be assessed prior to each treatment (within 24 hours of treatment) to ensure the following criteria are met:

- Platelets $> 75 \times 10^9/L$
- Neutrophils $> 1.0 \times 10^9/L$
- Bilirubin $< 1.5 \times ULN$
- Creatinine clearance (CrCL) (Cockcroft-Gault) $\geq 30 \text{ ml/min}$.
- ALT/AST $\leq 1.5 \times ULN$ on Cycle 1 day1; thereafter $\leq 3 \times ULN$

Please also refer to Section 7.5 for dose delays and modifications, and to section 7.7 for concomitant medications.

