Grade 2 Mild to moderate new symptoms	Withhold avelumab therapy Pulmonary and Infectious Disease consults Monitor symptoms daily, consider hospitalisation 1.0 to 2.0 mg/kg/day prednisolone or equivalent Add prophylactic antibiotics for opportunistic infections Consider bronchoscopy, lung biopsy	Re-assess every 1 to 3 days If improves: When symptoms return to Grade ≤1, taper steroids over at least 1 month and then resume avelumab therapy following steroids taper If not improving after 2 weeks or worsening: Treat as Grade 3 to 4
Grade 3 to 4 Grade 3: Severe new symptoms; New / worsening hypoxia; Grade 4: life-threatening	Permanently discontinue avelumab therapy Hospitalize Pulmonary and Infectious Disease consults 1.0 to 2.0 mg/kg/day prednisolone or equivalent Add prophylactic antibiotics for opportunistic infections Consider bronchoscopy, lung biopsy	If improves to Grade ≤1: Taper steroids over at least 1 month If not improving after 48 hours or worsening: Add additional immunosuppression (for example, infliximab, cyclophosphamide, IV immunoglobulin, or mycophenolate mofetil)
Hepatic AEs		
Inform the CI and trials office immediately if the treating investigator has concerns over liver function or liver involvement by lymphoma		
Grade of Liver Test Elevation (NCI-CTCAE v4.03)	Management	Follow-up
Grade 1	Continue avelumab therapy	Continue liver function

Grade 1 AST or ALT > ULN to 3.0 x ULN and / or total bilirubin > ULN to 1.5 x ULN		monitoring If worsens: Treat as Grade 2 or 3 to 4
Grade 2 AST or ALT > 3.0 to \leq 5 x ULN and / or total bilirubin > 1.5 to \leq 3 x ULN	Withhold avelumab therapy Increase frequency of monitoring to every 3 days 1.0 to 2.0 mg/kg/day prednisolone or equivalent	If returns to Grade \leq 1: Taper steroids over at least 1 month, : resume routine monitoring, resume avelumab therapy following steroids taper If elevations persist > 5 to 7 days or worsens: Treat as Grade 3 to 4.

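### Section 4.1 admits patients whose bilirubin is raised by Gilbert's syndrome, but the pre-dose check in 7.2 and the hepatic rows of Table 4 make no allowance for them

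*Combined protocol and SAP*

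**What the plan says.** **Eligibility.** Section 4.1 and the synopsis require total bilirubin of at most 1.5 x ULN and state that "patients with elevated bilirubin due to Gilbert's syndrome are eligible". No upper cap is given for these patients.

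**Pre-dose check.** Section 7.2 introduces its list with "The full blood count should be assessed prior to each treatment (within 24 hours of treatment) to ensure the following criteria are met". One of the criteria is "Bilirubin $< 1.5 \times ULN$", that is, strictly below 1.5 x ULN. No exemption is attached. For further handling the section says "Please also refer to Section 7.5 for dose delays and modifications".

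**Dose modification.** In the hepatic part of Table 4 (7.5.4), the Grade 1 row ("total bilirubin > ULN to 1.5 x ULN") continues avelumab. The Grade 2 row ("total bilirubin > 1.5 to \leq 3 x ULN") withholds it and starts prednisolone at 1.0 to 2.0 mg/kg/day. Above 3 x ULN treatment stops permanently. None of these rows refers to the patient's baseline.

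**Analysis.** Section 12.2 divides responders by all registered patients and counts those who are not assessable as non-responders. The per protocol population requires eligibility and at least one dose.

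**The concern.** The same protocol lets a patient in because a raised bilirubin is explained by a known benign condition, then applies a dosing limit that the same bilirubin fails. These are two stated rules that conflict, not a detail left out.

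At stake is mainly the conduct of the trial. A site that has enrolled such a patient must hold the drug, depart from 7.2, or seek ad hoc advice, and sites may choose differently. A patient with relapsed or refractory PTCL could be registered and then not treated. If Table 4 is read literally, the patient could also be given steroids for a value present before any avelumab, although 7.7 restricts steroid use because of its effect on T cells. The analytic consequence is secondary: an undosed patient counts in the response denominator but not in the per protocol population.

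**Working it through.** The plan states no figure on this point, so the check is a comparison of rules.

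**Step 1: when the exemption has effect.** At or below 1.5 x ULN a patient meets 4.1 without it. The exemption therefore changes the outcome only above 1.5 x ULN. This is an inference, since the text says only that bilirubin is elevated, but no other reading gives the parenthesis a function.

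**Step 2: follow one patient.** Take a patient with Gilbert's syndrome and a stable bilirubin of 2.0 x ULN (an assumed value).

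| Rule | Condition | Result at 2.0 x ULN |
|---|---|---|
| 4.1 and synopsis | at most 1.5 x ULN, or Gilbert's syndrome | eligible |
| 7.2, every dose from cycle 1 day 1 | below 1.5 x ULN | fails |
| Table 4, hepatic Grade 2 | above 1.5 and up to 3 x ULN | withhold, steroids |

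Above 3 x ULN the last row becomes permanent discontinuation.

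**Step 3: look for text that lifts the check.**
- Section 7.3.1 puts bilirubin in the biochemistry taken in the 24 hours before each dose, so the value will be seen every time.
- Section 7.5.6 adjusts for raised baseline bilirubin, but only to identify potential Hy's law cases, in combination with AST/ALT. It does not govern dosing.
- Table 5 (7.8) excepts certain single laboratory values that resolve within 7 days. A stable raised value does not resolve, and the exception does not mention 7.2.
- The ALT/AST line of 7.2 was tailored: it matches 4.1 at cycle 1 day 1 and relaxes to 3 x ULN afterwards. The bilirubin line has no such tailoring.

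Nothing found removes the conflict.

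**Step 4: extent for an affected patient.** 8 cycles x 2 doses = 16 planned checks. Each matters only if bilirubin is then at or above 1.5 x ULN.

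**Step 5: place in the analysis.** A patient who is never dosed and not assessable is one non-responder among those registered: 1/30 = 3.3% of the denominator, or 1/35 = 2.9%. The number of such patients cannot be derived from the documents.

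**Boundary value.** At exactly 1.5 x ULN a patient is eligible under 4.1 and is Grade 1 (continue) in Table 4, but fails 7.2. The correction can settle this too.

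**The case against.** The strongest reply is that a uniform limit before each dose may be deliberate. Amendment 3 changed the hepatic entry criteria for safety reasons, and a stricter rule at dosing than at entry is not in itself an error. That deserves weight in choosing the fix. It does not reconcile the text: if these patients were meant to be barred from treatment, the exemption in the current 4.1 would serve no purpose.

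It can also be said that Table 4 manages adverse events, and that 8.1.1 has pre-existing conditions reported only if they worsen by at least one grade. But 8.1.1 governs reporting, not dosing. It also counts a laboratory abnormality as an adverse event when it leads to interruption of study drug. The Table 4 hepatic rows are keyed to the grade of the liver test, so whether they apply to a stable raised value is not settled.

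Four stronger readings are tempting and are not supported:
- That sites have no rule for dosing these patients. They have one: 7.2 read literally says not to dose. What is missing is the exemption.
- That 7.1 ("All patients registered to the trial will receive avelumab at the dose of 10 mg/kg") is a second contradiction. It is a general statement of the regimen, subject to the 7.2 criteria.
- That the platelet and neutrophil signs are the same error, because 7.2 has "Platelets $> 75 \times 10^9/L$" where 4.1 accepts exactly 75. Section 4.1 sets the haematology limits at registration and 7.2 sets them before each dose, so they may differ. Section 7.5.5 also gives a route for treatment-related falls.
- That the response rate is distorted. No count of affected patients is available, so this cannot be shown.

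**Conclusion.** The conflict is real and minor. Sections 4.1 and 7.2 cannot both work as intended for a patient admitted through the Gilbert's exemption, and Table 4 has the same gap. Such a patient can be registered but not dosed while bilirubin stays at or above 1.5 x ULN, and still counts in the primary response denominator.

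This rests on two conditions: the exemption is meant to operate above 1.5 x ULN, and the 7.2 criteria are applied as written. The number affected is unknown and may be zero, and no decision threshold is shown to be crossed. Rarity limits the severity but does not resolve the conflict.

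**What to change.** Replace the bilirubin line in 7.2 with:

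> Bilirubin at most 1.5 x ULN, except in patients with Gilbert's syndrome admitted under 4.1. These may be dosed if total bilirubin has not worsened from their screening baseline (for example by 1 CTCAE grade, or by a tighter margin set by the clinical team) and ALT/AST meet the limits in this section.

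Make the matching change in the Table 4 hepatic rows, so that bilirubin in these patients is judged against baseline. This part is not optional: if only 7.2 changes, the Grade 2 row still withholds the drug and gives steroids.

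One grade is the worsening standard already used in 8.1.1, but it is coarse as a dosing margin. On the Table 4 bands, a baseline of 2.0 x ULN could rise by 3.0 - 2.0 = 1.0 x ULN before changing grade, and a baseline of 1.6 x ULN by 3.0 - 1.6 = 1.4 x ULN (both baselines assumed). Table 4 also merges Grades 3 and 4, so for a baseline above 3 x ULN it offers no further bilirubin boundary. A numeric margin would be clearer. The 7.5.6 bilirubin threshold should not be borrowed for it, since it is one part of a combined trigger.

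Cost: edits in two places, 7.2 and Table 4, and clinical agreement on the margin, in the next substantial amendment. Eligibility, sample size and analysis are unchanged. The downside is that a liver hold is relaxed for a few patients, so the ALT/AST limits and the 7.5.6 evaluation should stay in force. If the clinical team wants the hold to apply to everyone, the consistent alternative is to remove the exemption from 4.1 and the synopsis.
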